#### 3.2 SECONDARY EFFICACY ENDPOINTS

- The responder rate as identified by the Outcomes Measures for Rheumatic Arthritis Clinical Trials-Osteoarthritis Research Society International (OMERACT-OARSI) responder index at 26 weeks post treatment comparing the Cingal® arm to the TH arm and Placebo arm, the Cingal arm to the Placebo arm, and the TH arm to the Placebo arm.
- The change from Baseline in knee pain as measured by daily VAS Pain Score and average weekly VAS Pain Score (100 mm VAS) through 26 weeks post treatment comparing the Cingal® arm to the TH arm and Placebo arm, the Cingal arm to the Placebo arm, and the TH arm to the Placebo arm.
- The change from Baseline in knee pain as measured by daily NRS Pain Score and average weekly NRS Pain Score (0-10 NRS) through 26 weeks post treatment comparing the Cingal® arm to the TH arm and Placebo arm, the Cingal arm to the Placebo arm, and the TH arm to the Placebo arm.
- The change from Baseline in WOMAC Physical Function score at 26 weeks post treatment comparing the Cingal® arm to the TH arm and Placebo arm, the Cingal arm to the Placebo arm, and the TH arm to the Placebo arm.

- The change from Baseline in WOMAC Stiffness score at 26 weeks post treatment comparing the Cingal® arm to the TH arm and Placebo arm, the Cingal arm to the Placebo arm, and the TH arm to the Placebo arm, the Cingal arm to the Placebo arm, and the TH arm to the Placebo arm.
- The change from Baseline in Total WOMAC score at 26 weeks post treatment comparing the Cingal® arm to the TH arm and Placebo arm, the Cingal arm to the Placebo arm, and the TH arm to the Placebo arm.
- The change from Baseline in the Patient Global Assessment at 26 weeks post treatment in the Cingal® arm compared to the TH arm and Placebo arm, the Cingal arm to the Placebo arm, and the TH arm to the Placebo arm.
- The change from Baseline in the Evaluator Global Assessment at 26 weeks post treatment in the Cingal® arm compared to the TH arm and Placebo arm, the Cingal arm to the Placebo arm, and the TH arm to the Placebo arm.
- The usage of rescue medication through 26 weeks post treatment in the Cingal® arm compared to the TH arm and Placebo arm, the Cingal arm to the Placebo arm, and the TH arm to the Placebo arm.

#### 3.3 EXPLORATORY ENDPOINTS

Any comparisons between arms (Cingal®, TH, Placebo), within arms and / or time points (from baseline through to 26 weeks) not described in the primary or secondary endpoints may be presented in the exploratory endpoints including:

- EuroQoL (EQ-5D-5L)
- WOMAC Pain Score (100mm VAS)
- Daily VAS pain scores & weekly average VAS pain scores
- Daily NRS pain scores & weekly average NRS pain scores
- OMERACT-OARSI
- Total WOMAC
- WOMAC Stiffness Score
- WOMAC Physical Function
- Patient Global Assessment
- Evaluator Global Assessment
- Range of Motion
- Rescue Medication Use
- Number of Treatment Failures

## *3.4 SAFETY ENDPOINT:*

The incidence, timing, severity, and relationship to treatment of all Adverse Events (AE) will be collected and coded using Medical Dictionary for Regulatory Activities (MedDRA). Local injection site and non-local events will be recorded separately.

### 4.0 Statistical Methods in Protocol

#### 4.1 STATISTICAL METHODS

This Statistical Analysis Plan provides the details of the statistical analysis of the study data that is described in the protocol.

# 4.1.1 Sample Size

This is a pilot study designed to estimate as the primary assessment, the differences between Cingal and Triamcinolone Hexacetonide (TH) with respect to the difference in the change in WOMAC pain score from baseline to 26 weeks post treatment. For convenience the sample size will be assessed in a 3:3:1 ratio (Cingal: TH: Placebo) with the sample sizes being 99:99:33, for a total sample size of 231 patients treated. It should be noted that if the standard deviation for the difference in change from baseline in the WOAMC Pain Score between Cingal and TH is approximately 20 points and a difference of 8 points would yield 80% power of detecting that difference. If the difference is 10 points, this sample size yields over 90% power of detecting that difference.

Since the primary analysis in this study is an intent to treat analysis and the missing data for a patient will be imputed using mixed effects models, no dropout rate will be assumed for this study. Thus, the total sample size will be 231 patients treated.

# 4.1.2 Primary Efficacy Endpoint

4.1.2.1 The primary efficacy endpoint is the change from baseline in knee pain as measured by the WOMAC Pain Score (1 00 mm VAS) at 26 weeks post treatment comparing the Cingal Arm to the triamcinolone hexacetonide (TH) Arm, the Cingal Arm to the Placebo Arm, and the TH Arm to the Placebo Arm

Data will be analyzed via an analysis of variance (ANOVA) with a term for treatment and baseline pain score as a covariate. The primary hypothesis(es) will be tested by a predefined contrast for comparing the Cingal Arm to the triamcinolone hexacetonide (TH) Arm, the Cingal Arm to the Placebo Arm, and the TH Arm to the Placebo Arm. Formally, the hypotheses to be tested is:

```
H_0: μ_{DC} = μ_{DT} versus H_A: μ_{DC} ≠ μ_{DT}. (Primary Cingal to TH) H_0: μ_{DC} = μ_{DP} versus H_A: μ_{DC} ≠ μ_{DP}. (Primary Cingal to Placebo) H_0: μ_{DT} = μ_{DP} versus H_A: μ_{DT} ≠ μ_{DP}. (Primary TH to Placebo)
```

Where  $\mu_{DC}$  is the mean change from baseline in the WOMAC Pain Score for the Cingal Arm at 26 weeks,  $\mu_{DT}$  is the mean change from baseline in the WOMAC Pain Score for the triamcinolone hexacetonide Arm at 26 weeks, and  $\mu_{DP}$  is the mean change from baseline in the WOMAC Pain Score for the Placebo Arm at 26 weeks. Since there are three treatment groups in this study, this hypothesis will be tested using a one way ANOVA and constructing a contrast for this hypothesis.

This process is the same as using a baseline pain adjusted two-sample t-test with the common variance estimate from the ANOVA.

The anticipated SAS code for this analysis is given as:

The mean difference will be estimated and tested using the contrasts from PROC GLM on the responses at the 26 week time period.

```
PROC GLM DATA=EFF;
WHERE VISITNO = 26;
CLASS TRT;
MODEL WOMDIFF = BASEWOM TRT / TYPE3 ALPHA=0.05;
ESTIMATE 'CINGAL VS PLACEBO' TRT 1 -1 0;
ESTIMATE 'CINGAL VS TH' TRT 1 0 -1;
ESTIMATE 'PLACEBO VS TH' TRT 0 1 -1;
LSMEANS TRT / DIFF CL ALPHA=0.05;
FORMAT TRT TRTF.;
RUN;
```

In this model, the WOMDIFF is the difference in WOMAC Pain Scores from baseline. The variable TRT is a categorical variable where 1 = Cingal, 2=Placebo, and 3=TH. The variable BASEWOM is the baseline WOAMC scores and the variable VISITNO is the visit number identifier. ODS statements will be used to output the contrasts and the mean differences into data sets that can be easily displayed using PROC REPORT. The primary analysis will be comparing Cingal to TH.

The tables for this analysis will be displayed as:

Summary of Least Squares Means at 26 weeks – WOMAC Pain Score

Treatment Group	Mean Percent Improvement LS Mean	Standard Error
Cingal		
Placebo		
TH		

Summary of Differences in Mean Responses at 26 Weeks – WOMAC Pain Score

Treatment Group	Mean Percent Improvement	Standard Error	Lower Confidence Limit	Upper Confidence Limit	p-value
Cingal – Placebo					
Cingal – TH (Primary)					
Placebo - TH					

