- 25. Subject has a decrease of ≥ 20 mm in the WOMAC pain-sub-score (average of 5 pain scales) from Screening to Baseline in the Index knee on a 100 mm Visual Analog Scale (VAS) scale.
- 26. Subject has a synovial fluid aspirate volume > 10 mL in the Index knee.
- 27. Subject has a contraindication to continue with the study treatment injection based on the visual appearance of the synovial fluid aspirate unless the fluid is examined microscopically prior to injection with no clinically significant findings (e.g. bacteria, crystals or blood).
- 28. Subject has range of motion of less than 100° flexion in either knee.

Criteria for Evaluation

Efficacy:

Primary Endpoint:

 The change from Baseline in knee pain as measured by the WOMAC Pain Score (100 mm VAS) at 26 weeks post treatment comparing the Cingal® arm to the TH arm, the Cingal arm to the Placebo arm, and the TH arm to the Placebo arm.

Secondary Endpoints:

- The responder rate as identified by the Outcomes Measures for Rheumatic Arthritis Clinical Trials-Osteoarthritis Research Society International (OMERACT-OARSI) responder index at 26 weeks post treatment comparing the Cingal® arm to the TH arm, the Cingal arm to the Placebo arm, and the TH arm to the Placebo arm.
- The change from Baseline in knee pain as measured by daily VAS Pain Score and average weekly VAS Pain Score (100 mm VAS) through 26 weeks post treatment comparing the Cingal® arm to the TH arm, the Cingal arm to the Placebo arm, and the TH arm to the Placebo arm.
- The change from Baseline in knee pain as measured by daily NRS Pain Score and average weekly NRS Pain Score (0-10 NRS) through 26 weeks post treatment comparing the Cingal® arm to the TH arm, the Cingal arm to the Placebo arm, and the TH arm to the Placebo arm.
- The change from Baseline in WOMAC Physical Function score at 26 weeks post treatment comparing the Cingal® arm to the TH arm, the Cingal arm to the Placebo arm, and the TH arm to the Placebo arm.
- The change from Baseline in WOMAC Stiffness score at 26 weeks post treatment comparing the Cingal® arm to the TH arm, the Cingal arm to the Placebo arm, and the TH arm to the Placebo arm.
- The change from Baseline in Total WOMAC score at 26 weeks post

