11 STATISTICAL CONSIDERATIONS

The statistical analysis of the study is described in detail in a separate version-controlled prospective Statistical Analysis Plan (SAP). However, the statistical methodology described in this section of the protocol will be the basis for the detailed SAP. It should be noted that this is a pilot study designed to assess the differences between Cingal and TH for change in pain and function scores between Baseline and 26 weeks post treatment. This change in scores will be conducted on multiple assessments and therefore, no formal hypothesis testing will be performed.

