11.2 Primary Efficacy Endpoint

The primary efficacy endpoint is the change from Baseline in knee pain as measured by the WOMAC Pain Score (100 mm VAS).

The time point of main interest is 26 weeks, but in order to study the time course profile, the data will be analyzed at each time point. Data will be analyzed via an Analysis of Variance (ANOVA) with a term for treatment and Baseline pain score as a covariate. The primary analysis will be conducted by constructing 95% confidence intervals using the predefined contrasts for comparing the Cingal® arm to the TH arm, the Cingal arm to the Placebo arm, and the TH arm to the Placebo arm. These confidence intervals will be constructed as:

$$(\overline{X}_{\iota} - \overline{X}_{J}) \pm z_{\alpha/2} s_{D}$$

Where $\overline{X_i}$ and $\overline{X_j}$ are the Least Squares Means for the two treatments being utilized and s_D is the standard deviation of that difference.

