11.3 Secondary Efficacy Endpoints

There are many secondary endpoints to be investigated in this study. Again, these endpoints will be evaluated utilizing pairwise confidence intervals. For continuous variables the confidence intervals will be constructed as in section 11.2. For the dichotomous variables, the confidence intervals for the responder rates will be constructed utilizing the normal approximation to the binomial.

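### The protocol plans 95% confidence intervals without formal testing of change scores; the SAP tests three contrasts per endpoint at an unadjusted 5%, tags them 'Primary' inconsistently, and omits several planned analyses

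*SAP*

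**What the plan says.** **Protocol.** Section 11 states: "This change in scores will be conducted on multiple assessments and therefore, no formal hypothesis testing will be performed". It adds that "the statistical methodology described in this section of the protocol will be the basis for the detailed SAP". Section 11.2 says "The primary analysis will be conducted by constructing 95% confidence intervals using the predefined contrasts", and that "in order to study the time course profile, the data will be analyzed at each time point". Section 11.3 carries this over to the secondary endpoints: "Again, these endpoints will be evaluated utilizing pairwise confidence intervals". The primary endpoint (Synopsis, 6.1) lists Cingal vs TH and then "the Cingal arm to the Placebo arm, and the TH arm to the Placebo arm", without ranking them. The sample size section (11.1) covers Cingal vs TH only.

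**SAP.** Section 4.1 says: "This Statistical Analysis Plan provides the details of the statistical analysis of the study data that is described in the protocol". Section 4.1.2 nevertheless says: "The primary hypothesis(es) will be tested by a predefined contrast for comparing the Cingal Arm to the triamcinolone hexacetonide (TH) Arm", and continues with the two placebo contrasts. It writes out three two-sided hypotheses, each tagged 'Primary'. Its text then closes by naming Cingal vs TH as the primary analysis, and the results shell marks only that row. Section 4.1.3.2 repeats all three tags for the secondary endpoints. Section 4.2 sets every test and interval at 5%, and no multiplicity rule appears anywhere.

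**The concern.** The two documents disagree on which results can support a claim. Under the protocol no change-score contrast is tested. Under the SAP's tags, a placebo contrast with p < 0.05 could be reported as a significant primary result, even if Cingal and TH did not differ.

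Deleting the p-values would not settle this. Three unadjusted 95% intervals, each read for whether it excludes zero, carry the same error. What is missing is a statement of which comparison is primary and how the others are to be read. The ambiguity starts in the endpoint wording, which lists three unranked comparisons in both documents. Protocol 11.3.8 and 11.3.9 add to it by calling the intervals of two secondary endpoints the primary analysis.

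An analyst who follows the SAP would also leave out intervals that the protocol promises. These include the time course, which the duration part of the study objective needs.

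**Working it through.** **1. The plan's own figure.** Inputs from Protocol 11.1 and SAP 4.1.1: 99, 99 and 33 subjects; SD 20; differences of 8 and 10 points; no dropout. I read the SD as that of the change score within an arm and assume it is equal in all arms; this reading reproduces the stated power.

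- SE for Cingal − TH = 20·√(1/99 + 1/99) = 2.84 mm
- Noncentrality at 8 mm = 8/2.84 = 2.81. Power at two-sided 5% (noncentral t, 227 df) = 80.0%; at 10 mm it is 93.9%.

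The stated 80% and over 90% are therefore correct, for one comparison at an unadjusted 5%.

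**2. The placebo contrasts.** SE = 20·√(1/99 + 1/33) = 4.02 mm. Power is 51% at 8 mm and 70% at 10 mm, so the stated power does not extend to them.

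**3. False-positive chance if any of the three could be claimed.** Simulation of 4,000,000 trials with all arms equal, 99/99/33, pooled variance, 227 df:

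| Event | Probability |
|---|---|
| Cingal vs TH significant | 5.0% |
| At least one of three significant | 11.9% |
| A placebo contrast significant, Cingal vs TH not | 11.9% − 5.0% = 6.9% |

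The figure is below the independent-test value, 1 − 0.95³ = 14.3%, because the contrasts share arms. The two placebo contrasts correlate at (1/33)/(1/99 + 1/33) = 0.75. If Cingal equals TH and both differ from placebo, the only true null is Cingal vs TH and the error is 5%.

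**4. Interval widths and the price of three co-equal primaries.** Pointwise multiplier t(0.975, 227) = 1.970; simultaneous multiplier (95th percentile of the largest |t|) = 2.349.

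| Contrast | Pointwise half-width | Simultaneous half-width |
|---|---|---|
| Cingal − TH | 1.970 × 2.84 = 5.6 mm | 2.349 × 2.84 = 6.7 mm |
| Each vs placebo | 1.970 × 4.02 = 7.9 mm | 2.349 × 4.02 = 9.4 mm |

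With the simultaneous multiplier, Cingal vs TH power at 8 mm falls from 80% to 68%.

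**5. Secondary tests in the SAP.** OMERACT-OARSI, VAS, NRS, physical function, stiffness, total WOMAC, Patient Global and rescue use: 8 × 3 = 24 unadjusted tests, more if daily and weekly scores are counted separately.

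**6. Planned analyses against the SAP's methods.**

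| Protocol | SAP |
|---|---|
| 11.3.1: intervals for responder-rate differences | 4.1.3.1: Fisher p-values only |
| 11.3.2, 11.3.3: AUC and repeated-measures ANOVA of weekly VAS and NRS | 4.1.3.2: neither specified |
| 11.3.8: Evaluator Global Assessment, ANOVA with intervals | Secondary in 3.2, absent from 4.1.3.2, optional exploratory item in 4.1.4 |
| 11.3.9: rescue use, ANOVA with intervals | 4.1.3.9: Fisher's test on the percentage of users |
| 11.2 and 11.3.1–11.3.9: analysis at each time point | Code and shells use week 26 only; other visits optional in 4.1.4 |

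**7. Shell headings.** The modelled outcome in SAP 4.1.2 and 4.1.3.2 is the raw difference from baseline, but the shells head its LS means and their differences as a mean percentage improvement.

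**The case against.** The 11.9% is a worst case. It needs all arms equal and a rule that any one of three contrasts may be claimed, and no sentence states that rule. The closing sentence of SAP 4.1.2, the shells and both sample size sections point to Cingal vs TH, and the stated purpose of the placebo arm is to set subjects' expectations. This stands as a limit on size: if that sentence governs, the error is 5.0%. But the tags in the same section contradict it, and nothing says how to read the other contrasts.

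'Omitted' also needs qualifying:

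- SAP 4.5 mentions a mixed-effects repeated-measures analysis, but to justify the missing-data approach; it specifies nothing for VAS, NRS or AUC.
- SAP 4.1.4 keeps Evaluator Global and pill counts, but only as optional or descriptive items.
- The protocol's exploratory sections contain the same permissive clause about other time points. That does not override the firm commitment to every time point in 11.2 and 11.3.

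The protocol's own intervals are unadjusted too, so the SAP did not create the multiplicity; it added formal tests and p-values. Calling the intervals in 11.3.8 and 11.3.9 the primary analysis may be copied text, and the shell headings are slips. Both are minor beside the rest, but cheap to correct.

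**Conclusion.** The concern holds and should be fixed. The SAP departs from the protocol section it is meant to detail, contradicts itself on what is primary, and gives no secondary method for several planned analyses. The false-positive chance is 5.0% or 11.9% depending on which part of SAP 4.1.2 is followed; the higher figure assumes equal arms and any-of-three claiming. The widths and power figures assume SD 20 in every arm and no dropout. The sample size itself is sound for Cingal vs TH. Week-26 estimates for continuous endpoints analysed in both documents barely change; the consequences lie in claims, labels and omitted results.

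**What to change.** 1. State in both documents that Cingal vs TH at week 26 is the only primary comparison, reported as the difference in LS-mean change in mm with its 95% interval. If a test is kept, make it this one at two-sided 5% and amend Protocol 11. If none is kept, restate the power sentences as precision (half-width 5.6 mm at SD 20).
2. Remove the 'Primary' tag from the placebo contrasts in SAP 4.1.2 and from every secondary endpoint in 4.1.3. Make the placebo contrasts supportive in the endpoint wording (Synopsis, Protocol 6.1 and 11.2, SAP 3.1 and 4.1.2), and correct Protocol 11.3.8 and 11.3.9.
3. Report placebo contrasts and secondary endpoints as nominal 95% intervals, state that exclusion of zero supports no confirmatory claim, and align SAP 4.2.
4. Restore in the SAP the responder-difference intervals, Evaluator Global Assessment, AUC and repeated-measures analyses, and the analyses at each time point. Restore the rescue-use ANOVA too, or amend Protocol 11.3.9.
5. Head the first shell 'LS-mean change from baseline' and the second 'Difference in LS-mean change', in the endpoint's units.

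Cost: SAP text and shells, plus a few protocol sentences, which need FDA and IRB approval under Protocol 15.4. No new data; the 80% power is kept. The unadjusted p-values for placebo contrasts and secondary endpoints are lost. The change should be made before unblinding.

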# 4.1.3 Secondary Efficacy Endpoints

4.1.3.1 The responder rate as identified by the Outcomes Measures for Rheumatic Arthritis Clinical Trials-Osteoarthritis Research Society International (OMERACT-OARSI) responder index at 26 weeks post treatment comparing the Cingal® arm to the TH arm, the Cingal arm to the Placebo arm, and the TH arm to the Placebo Arm.

The response rate for the Cingal group and Triamcinolone Hexacetonide (TH) group will be calculated and tested using Fisher's exact test. Formally, the hypothesis to be tested is:

```
H0: \pi_C = \pi_T versus H0: \pi_C \neq \pi_T
```

Where  $\pi_C$  is the responder rate for the Cingal group and  $\pi_T$  is the responder rate for the triamcinolone hexacetonide group.

The response rate for the Cingal Arm, the Placebo Arm and Triamcinolone Hexacetonide (TH) Arm will be calculated and tested using Fisher's exact test. Formally, the hypotheses to be tested are:

```
H0: \pi_C = \pi_P versus H0: \pi_C \neq \pi_P
H0: \pi_T = \pi_P versus H0: \pi_T \neq \pi_P
```

Where  $\pi_C$  is the responder rate for the Cingal Arm,  $\pi_T$  is the responder rate for the triamcinolone hexacetonide Arm, and  $\pi_P$  is the responder rate for the Placebo Arm.

This will be estimated and tested using PROC FREQ with the EXACT option. The results will be displayed similar to:

Summary of the OMERACT-OARSI Responder Rates at 26 Weeks

Parameter	Cingal	Placebo	TH
Estimate n/N (%)			
Cingal vs TH (Primary) (p-value)			
Cingal vs Placebo (p-value)			
Placebo vs TH (p-value)			

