9.9.7 Early Termination due to lack of efficacy in the Index knee

If a subject wants to obtain additional treatments such as HA and steroid injection in Index knee, the subject should undergo below assessment before receiving the additional treatment:

- Concomitant Medications
- Assess Adverse Events

- Confirm Rescue Medication Washout
- Count Rescue Medication Pills
- Evaluate Subject Electronic Diary
- Physical Evaluation (Both Knees)
- ROM (Both Knees) to be performed by Blinded Evaluator
- Evaluator Global Assessment to be performed by Blinded Evaluator
- WOMAC (Both Knees)
- VAS Pain Scale (Both Knees)
- NRS Pain Scale (Both Knees)
- EuroQoL-5D-5L
- Patient Global Assessment

After completing the assessment, the subject should be terminated from the study. These subjects will be considered as Treatment Failure.

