11.3.1 OMERACT-OARSI responder

The OMERACT-OARSI response rates for the Cingal® arm, TH arm, and the Placebo arm will be calculated for each time point and all pairwise difference confidence intervals will be constructed utilizing the normal approximation to the binomial distribution [29, 30].

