### 4.5 SUBJECT POPULATIONS

All safety analyses will be conducted on all subjects who undergo treatment in any group.

The primary analysis on the primary endpoint will be performed on the ITT populations using the Multiple Imputation Methodology. The Multiple Imputation Methodology will use a mixed effects repeated measures model to predict the missing values. All Primary and Secondary endpoints will be analyzed using the ITT population.

It has been determined that any missing data in this study will follow the Missing at Random (MAR) assumption and is justified by the following section from the guide on missing data.

Missing Data Because of Attrition in the Course of the Study The longer the planned length of a clinical trial, the greater the chance that participants will drop out of the trial due to their moving out of the area or otherwise experiencing changes in their lives that preclude or complicate further participation. If dropping out due to these situations is known to be unrelated to changes in health status, an MAR assumption for the missing values seems justified;

Since none of these patients are likely to be in a life threatening disease situation and many have had knee pain for a period of time, the missing data will unlikely be due to any treatment effect or lack thereof. Previous studies have demonstrated a missing data rate of less than 1%. Thus, any missing data in this study follows that paradigm and thus should be considered MAR. Under this MAR assumption, the mixed effects repeated measures analysis yields unbiased estimates of the treatment effects and thus will be utilized in the analysis.

A secondary analysis will be conducted on the Per Protocol (PP) population. Since the primary endpoint is at 26 weeks, this is all subjects who complete the 26 week visit and who are not major violators of the protocol. For all other visits, this is defined as the subjects who complete those visits according to the protocol.

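### SAP 4.1.3.1 replaces the protocol's confidence intervals for OMERACT-OARSI response differences with week-26 Fisher p-values, and gives no rule for missing responder status

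*SAP*

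**What the plan says.** Protocol 11 calls the trial a pilot and states that "no formal hypothesis testing will be performed". Protocol 11.3 says of the secondary endpoints that "these endpoints will be evaluated utilizing pairwise confidence intervals". For OMERACT-OARSI, Protocol 11.3.1 has response rates calculated at each time point and adds that "all pairwise difference confidence intervals will be constructed utilizing the normal approximation to the binomial distribution".

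SAP 4.1.3.1 writes null and alternative hypotheses for the three pairs of arms at week 26 and says the rates "will be calculated and tested using Fisher's exact test". The only software instruction is "This will be estimated and tested using PROC FREQ with the EXACT option". The table shell has one row of n/N (%) by arm and three p-value rows, the first of which begins "Cingal vs TH (Primary) (p-value". It has no row for a difference or for confidence limits. Other time points appear only as optional exploratory comparisons in SAP 4.1.4, where discrete variables are again assigned Fisher's exact test.

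On missing data, SAP 4.5 says "All Primary and Secondary endpoints will be analyzed using the ITT population". It names multiple imputation for the primary endpoint, as Protocol 11.8 does, whereas the protocol synopsis applies it to the endpoints generally. Protocol 9.9.7 covers subjects who leave for lack of efficacy in the index knee: they are assessed, then terminated from the study, and "These subjects will be considered as Treatment Failure".

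**The concern.** The study exists to estimate differences between arms. A rate per arm with a p-value does not show how large the difference is or how uncertain it is, and it presents as tests what the protocol calls estimation. The SAP tables for continuous endpoints do have confidence-limit columns, so the omission is specific to the Fisher-tested endpoints.

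Missing week-26 status is the second gap. Some of it would be related to outcome by design, because a subject who leaves for lack of efficacy before week 26 has no week-26 score. A Fisher p-value carries no estimate and variance for Rubin's rules, and the SAP names no other way to combine results. If PROC FREQ were run on unimputed data, subjects with missing status would fall out of n/N. That is a risk of an observed-case analysis that loses known failures from the denominator.

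**Working it through.** **1. The plan's own figure.** The documents give no power or precision for OMERACT-OARSI. The one figure they give concerns WOMAC pain (Protocol 11.1, SAP 4.1.1): 99 per arm, SD 20, two-sided 5%. The standard error is 20 × √(2/99) = 2.843. Power at 8 points is Φ(8/2.843 − 1.96) = 0.804; at 10 points it is Φ(10/2.843 − 1.96) = 0.940. The stated 80% and over 90% reproduce, but they do not bear on this endpoint.

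**2. The two documents side by side.**

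| | Protocol 11, 11.3, 11.3.1 | SAP 4.1.3.1 |
|---|---|---|
| Quantity | Pairwise differences in rate | Rate per arm |
| Inference | Confidence interval, normal approximation | Fisher's exact test |
| Formal testing | None | Three hypotheses |
| Time | Each time point | Week 26 |

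**3. Precision that the planned table would not show.** Arm sizes are 99, 99 and 33 (SAP 4.1.1). Response rates are not given, so 50% to 80%, equal in both arms, is assumed. Half-width = 1.96 × √[p(1−p)(1/n₁ + 1/n₂)].

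- Cingal versus TH: 13.9 points at p = 0.5, 11.1 points at p = 0.8.
- Either active arm versus Placebo: 19.7 points at p = 0.5, 15.8 points at p = 0.8.

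Example with assumed counts 69/99 and 54/99: difference 15/99 = 15.2 points; standard error √(0.697×0.303/99 + 0.545×0.455/99) = 0.0681; 95% CI 1.8 to 28.5 points. The SAP table would show 69.7%, 54.5% and p = 0.040.

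**4. Fisher's test does not stand in for the interval.** By exact enumeration under equal true rates of 50% and 70%, two-sided error at 99 versus 99 is 3.5% to 3.9% for Fisher and 5.2% to 5.5% for the normal-approximation interval. At 99 versus 33 it is 3.8% to 4.4% and 5.9% to 6.2%. The two disagree about significance in about 1.5% to 2.4% of such null trials.

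**5. Combining over imputations.** Illustration with 20 imputations and observed rates near 70% and 56%:

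- 10% missing (62/89 and 50/89 observed): Fisher p runs from 0.012 to 0.186 across imputations. The risk difference pools by Rubin's rules to 13.7 points (95% CI −0.6 to 28.0).
- 1% missing (69/98 and 55/98 observed): Fisher p runs from 0.039 to 0.077. The pooled difference is 14.1 points (0.7 to 27.4).

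**6. What dropping missing status could do.** If terminated subjects count as non-responders, the rate in all subjects is the observed rate × (1 − fraction terminated). Assume 80% response among those observed in both arms, so the observed-case difference is 0.

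| Terminated, Cingal / TH | Rates in all subjects | Difference |
|---|---|---|
| 0 / 1 of 99 (about the SAP's 1%) | 80.0% / 79.2% | 0.8 points |
| 5% / 10% | 76% / 72% | 4 points |
| 10% / 20% | 72% / 64% | 8 points |

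With equal loss the shift in the difference is modest: 62/89 versus 50/89 differ by 13.5 points, and 62/99 versus 50/99 by 12.1. Only the first row of the table matches a missing rate quoted in the documents; the other rates are assumptions.

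**The case against.** The shell does print n/N (%) per arm, and the protocol's interval follows from those counts by arithmetic. That stands when there are no missing data: the loss is in reporting, on a secondary endpoint of a pilot. It does not remove the conflict, and with imputed data the interval could not be recovered from a single table.

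A reader might infer that the SAP's analysis defaults to completers. The documents do not support that. SAP 4.5 assigns secondary endpoints to ITT, and completing week 26 is part of the Per Protocol definition only. SAP 4.1.3.1 has no dataset, filter or code; the statement selecting visit 26 belongs to the PROC GLM analyses. Counting missing status as non-response, or deriving it from imputed scores, is as open as dropping it.

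A reader might also infer that these results cannot be pooled. That is too strong: the risk difference from the same tables pools directly. What is missing is the instruction. It is also unsettled whether multiple imputation was meant for this endpoint, since only the protocol synopsis extends it beyond the primary.

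Nor do failures disappear. Protocol 9.9.7 collects WOMAC and Patient Global Assessment at early termination, which can inform imputation, and the number of Treatment Failures is a listed exploratory endpoint. The SAP also quotes under 1% missing from previous studies, and the sample size assumes no dropout. These points limit the likely size of any bias but supply no rule for week-26 responder status.

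**Conclusion.** The contradiction between SAP 4.1.3.1 and Protocol 11, 11.3 and 11.3.1 is clear and holds with no missing data at all. As written, the SAP adds tests that the protocol disclaims, confines the secondary analysis to week 26, and omits the planned differences and intervals. At assumed rates of 50% to 80%, the unreported half-widths are 11.1 to 13.9 points for Cingal versus TH and 15.8 to 19.7 points against Placebo.

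The handling of missing responder status is a gap in specification, not a demonstrated bias. At the SAP's under 1%, the illustrated effect is about 0.8 points, small beside an 11-point half-width. It reaches 4 or 8 points only under assumed termination rates that are higher and differ by arm. Treating terminations for lack of efficacy as non-response is a choice of estimand; neither document states it for this endpoint, and it departs from their missing-at-random approach.

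**What to change.** In SAP 4.1.3.1:

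- Replace the hypotheses and p-value rows with the three pairwise risk differences and 95% confidence intervals by the protocol's method, at weeks 1, 3, 6, 12, 18 and 26, with week 26 as the main time point. Set N to all ITT subjects per arm.
- State that missing response is derived from the imputed component scores, and that the risk difference and its variance are pooled over imputations with PROC MIANALYZE. Align SAP 4.5 and Protocol 11.8 with the synopsis on whether multiple imputation covers this endpoint.
- Prespecify and report an analysis that counts subjects terminated for lack of efficacy as non-responders at later visits, labelled as an estimand choice.

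The cost is SAP text, one table shell and a little programming, settled before unblinding. Response rates may be lower when terminations count as non-response.
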